5.5 Total Number of Participants

Recruitment will end when approximately 24 participants are enrolled. It is expected that approximately 30 participants will be enrolled in order to produce 24 evaluable participants.

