5.6 Participant Withdrawal or Termination

5.6.1 Reasons for Withdrawal or Termination

Participants are free to withdraw from participation in the study at any time upon request. An investigator may terminate participation in the study if:

- Any clinical adverse event (AE) or other medical condition or situation occurs such that continued participation in the study would not be in the best interest of the participant
- The participant meets an exclusion criterion (either newly developed or not previously recognized) that precludes further study participation
- The participant fails to adhere to protocol requirements
- Subject withdraws consent
- Subject experiences excessive fatigue or discomfort

Abrupt withdrawal or termination from study will not affect participant safety or clinical management.

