5.6.2 Handling of Participant Withdrawals or Termination

The proposed study does not seek to obtain follow-up data. As such, withdrawn or terminated participants will not be contacted for further data collection for the given protocol. Replacement of withdrawn or terminated participants will follow with standard recruitment and retention policies outlined in 5.4 Strategies for Recruitment and Retention.

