10.2 Statistical Hypotheses

Primary endpoint. Exoskeletal support will increase RC in stroke participants. Paired t-test comparing RC from baseline to loading blocks.

Primary endpoint. Exoskeletal support will decrease MC in stroke participants. Paired t-test comparing MC from baseline to loading blocks.

Secondary endpoint. There will be an association between change in RC (or MC) and CST lesion load. Independent linear regressions (RC vs. CSTLL and MC vs. CSTLL).

Secondary endpoint. RC values in stroke participants will be less than RC values in healthy controls during baseline blocks (t-test). MC values in stroke participants will be greater than MC values in healthy controls during baseline blocks (t-test).

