10.3 Analysis Datasets

All participants will be included the analysis dataset. The analysis dataset will include all relevant variables:
Outcome variables

- Relative contribution (RC)
- Muscle contribution (MC)
- CST lesion load (CSTLL)

Independent variables

- Loading (via exoskeleton)

Demographic variables

- Age
- Height
- Weight
- Time since stroke (stroke only)
- Lesion type (hemorrhagic vs. ischemic)
- Arm length
- Handedness
- Fugl-Meyer score (stroke only)

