10.4.2 Analysis of the Primary Efficacy Endpoint(s)

Primary study objective (change in RC, MC)

- Two-way ANOVAs on RC are conducted with within-subjects factor block (baseline, loading, retention) and between-subjects factor cohort (healthy, stroke). Three-way ANOVAs on MC are performed with within-subjects factors block and muscle (deltoid, biceps) and between-subjects factor cohort.

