10.4.5 Adherence and Retention Analyses

Adherence to the protocol will be assessed, calculated, and verified by the study investigator, [name]. [name] is under full control of the administration of the intervention. The intervention dose has been verified in previous work to be safe for participants (Brunfeldt et al., in review). In the event of a participant's wish to discontinue the protocol before study endpoint, that individual's data will be removed from analysis.

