10.5 Sample Size

Study Hypotheses: (Primary study objective)

- A power analysis using a moderate effect size (Cohen's $f = 0.25 - 0.3$) on MC, power of 0.8, and significance level of 0.05 suggests a total sample of 20-28 participants (10-14 per group). This is consistent with previous work using shared cursor tasks in stroke (Brunfeldt et al., 2022; Ranganathan et al., 2019).

Study Hypotheses: (Secondary study objective)

- An *a priori* power analysis with an effect size $f^2 = 0.7-0.9$, a power of $1-\beta = 0.8$ and error probability $\alpha = 0.05$ results in a target sample size of 12-14 participants. The estimated effect size was directly calculated from a Partial $R^2 = 0.4648$ using data from a feasibility study currently in preparation for publication. This R^2 value was taken from the relationship between lesion load and the change in MC from baseline to loading conditions.

Assumptions used in calculations:

- Assumed normal distribution, or corrected to normal distribution (e.g., via log-transform)
- We plan to enroll 30 participants, with between 6-8 stroke participants not meeting inclusion/exclusion criteria. The final $N = 12$ endpoint accounts for these dropouts.
- Data from withdrawn participants will not be included in the final dataset. Only those who complete all procedures will be included in the final analyses.

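### Sections 10.3, 10.4.5 and 10.5 give three different analysis sets, and the strictest one discards complete baseline and loading RC data

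*Combined protocol and SAP*

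**What the plan says.** Three sections of the protocol describe who is analysed.

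- Section 10.3: "All participants will be included the analysis dataset".
- Section 10.4.5: if a participant wishes to discontinue before a point that the section does not define, "that individual's data will be removed from analysis".
- Section 10.5: withdrawn participants are left out of the final dataset, and "Only those who complete all procedures will be included in the final analyses".

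Section 10.1 states that there is no formal SAP, and no other section defines a set for each endpoint.

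The primary RC hypothesis in section 10.2 is tested by a "Paired t-test comparing RC from baseline to loading blocks". Section 10.4.2 gives a second description of the primary analysis: an ANOVA with three blocks (baseline, loading, retention) and cohort as factors. By sections 4.1 and 7.2, the retention block and then the MVC measurement come after loading. Section 7.1 lists the imaging download as a task for stroke participants.

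Among the grounds for ending participation, section 5.6.1 lists: "Subject experiences excessive fatigue or discomfort". On numbers, section 5.5 expects that "approximately 30 participants will be enrolled in order to produce 24 evaluable participants", and section 5.6.2 says "Replacement of withdrawn or terminated participants will follow with standard recruitment and retention policies".

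**The concern.** The three rules do not give the same set, and the strictest ties inclusion in every analysis to procedures that some analyses do not use. A participant can have all the RC data that the baseline-to-loading comparison requires and still be deleted for what happened afterwards.

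Two things are at stake. First, analysts who follow different sections could report different numbers of participants and different estimates. Section 10.6.1 provides no masking, and section 16.1 gives data collection and analysis to the same investigator, so the rule should be fixed before the data are seen. Second, the deletion may depend on the response being studied. Section 2.4.1 names arm fatigue and soft-tissue discomfort as risks of the exoskeleton, and fatigue or discomfort is a listed reason to stop. A completers-only result describes only people who got through the whole session.

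**Working it through.** **1. The plan's own numbers.** The sample-size arithmetic is not at fault. For the primary objective, take the repeated-measures form λ = f²·N·m/(1−ρ) with 2 groups and m = 3 blocks, df1 = 2 and df2 = 2(N−2). The documents give neither the correlation nor the sphericity correction, so ρ = 0.5 and ε = 1 are assumed.

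- f = 0.25, N = 28: λ = 0.0625 × 28 × 3/0.5 = 10.5, power 0.812.
- f = 0.30, N = 20: λ = 0.09 × 20 × 3/0.5 = 10.8, power 0.812.

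This matches the stated 20 to 28. Enrolment also matches: 24/(1 − 0.20) = 30. However, section 10.5 attributes the loss to 6 to 8 stroke participants who fail eligibility (30 − 6 = 24, 30 − 8 = 22). There is no separate allowance for early stopping.

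**2. The rules side by side.**

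| Participant | 10.3 | 10.4.5 | 10.5 | Data for the RC paired test |
|---|---|---|---|---|
| Chooses to stop after block 2 | in | out | out | complete |
| Stopped by the investigator after block 2 | in | not covered | out | complete |
| Finishes three blocks, lacks only MVC | in | out only if by own wish | out | complete |
| Finishes the session, imaging not obtained (stroke) | in | not covered | out, read literally | complete |
| Stops during block 2 | in | out if by own wish | out | incomplete |

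RC concerns reaching displacement (section 3.1), and hand position comes from the touch controllers (section 14.1). Section 4.1 says that MVC data normalise outcome measures but not which ones. The table assumes that this means the muscle measure (MC) and not RC.

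**3. Possible size for RC (illustration).** Let completers have mean change D and stoppers mean change kD, with c completers and s stoppers who all have blocks 1 and 2.

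Available-data mean = (c + s·k)·D/(c + s). Ratio of completers' mean to available-data mean = (c + s)/(c + s·k).

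| c, s | k = 0 | k = 2 |
|---|---|---|
| 10, 2 (not replaced) | 12/10 = 1.20 | 12/14 = 0.857 |
| 12, 2 (replaced) | 14/12 = 1.167 | 14/16 = 0.875 |
| 12, 1 (replaced) | 13/12 = 1.083 | 13/14 = 0.929 |

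The ratio is 1 if s = 0 or k = 1. Both s and k are assumptions, as the documents fix neither.

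**4. Power if deletions are not replaced.** With total N of 24, 22 and 20, the model in step 1 gives power 0.740, 0.697 and 0.648 at f = 0.25, and 0.886, 0.853 and 0.812 at f = 0.30. For the lesion-load regression, f² = 0.4648/(1 − 0.4648) = 0.868. With 12, 11 and 10 stroke participants, power is 0.828, 0.785 and 0.733. Replacement avoids this loss but leaves the ratios in step 3 different from 1.

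**The case against.** The best reply is that 10.3 is a single general sentence introducing a list of variables, while the two sections that deal with early stopping both exclude. Most analysts would let the specific rule govern, so the operative rule is completers-only, stated in advance. That makes the conflict easier to resolve, but it does not rescue the rule: completers-only is what discards usable RC data.

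Several narrower points stand.

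- Exclusion for a missed procedure rests on 10.5 alone, because 10.4.5 concerns only people who wish to discontinue.
- A classical three-block ANOVA loses anyone without block 3 whatever 10.5 says, though not someone who lacks only MVC.
- MC probably needs the MVC, which is collected last, so an early stopper may have no usable MC.
- Imaging availability is checked at screening (section 7.2.1), so losing a participant for that reason should be rare.
- Load is applied only in block 2. Someone who stops during that block lacks a complete RC pair, and no rewording recovers it.
- Few withdrawals are expected. Section 2.1 reports that 14 stroke survivors tolerated the procedures without incident, and section 2.4.1 describes self-paced reaches with regular breaks.
- The study is not randomised, so exclusions break no randomised comparison.

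These points limit how often the problem will arise and how much the change recovers. They do not reconcile the three sections.

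**Conclusion.** The concern holds. The sections contradict each other. Even with 10.5 taken as governing, the plan deletes people who have everything the paired RC test needs, for reasons that may be related to how they responded. The clearest cases are a participant who stops after block 2 and one who lacks only the MVC. The effect on the estimate cannot be determined from the documents in size or direction. In the illustration the completers' mean lies between 14% below and 20% above the available-data mean with two unreplaced stoppers in 12, and between 7% below and 8% above with one replaced stopper. It is zero with none. These figures assume that stoppers have complete blocks 1 and 2 and that RC does not depend on the MVC. The bias is probably small if withdrawals are few, but with 12 people per group one or two matter. The point should be corrected; it does not undermine the design.

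**What to change.** Replace the statements in 10.3, 10.4.5 and 10.5 with one analysis set per endpoint:

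- **RC:** every eligible enrolled participant with usable block 1 and block 2 data.
- **MC:** the same, plus whatever normalising data the MC formula requires (the MVC, if it does). State the formula's needs.
- **Lesion-load regressions:** the relevant change score plus usable imaging.

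Keep data collected before withdrawal unless the participant withdraws permission for their use, in words consistent with section 13.4, which already lets the investigator use information gathered before authorisation is revoked. For the three-block ANOVA, either use all available blocks, for example in a mixed model, or say plainly that it is a complete-case analysis. Report withdrawals by group, block and reason, so that those lost during block 2 are visible, and give the completers' result as a sensitivity analysis.

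The cost is rewording three sections, a little more analysis, and slightly different numbers of participants across endpoints. No additional data are collected.

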10.6 Measures to Minimize Bias

10.6.1 Enrollment/Randomization/Masking Procedures

Enrollment will be initiated by the study investigator, [name]. [name] will contact participants via phone, SendSafe Secure email, or MyChart. Stroke participants will be contacted if they meet the inclusion criteria and assigned to the stroke group. Healthy control participants will be recruited on a rolling basis to match the age and gender of the stroke group. There is no randomization, blinding, or masking proposed.

11 Source Documents and Access to Source Data/Documents

Source data is all information, original records of clinical findings, observations, or other activities in a clinical trial necessary for the reconstruction and evaluation of the trial. Source data are contained in source documents.

Examples of these original documents, and data records include: hospital records, clinical and office charts, laboratory notes, memoranda, subjects' diaries or evaluation checklists, pharmacy dispensing records, recorded data from automated instruments, copies or transcriptions certified after verification as being accurate and complete, microfiches, photographic negatives, microfilm or magnetic media, x-rays, subject files, and records kept at the pharmacy, at the laboratories, and at medico-technical departments involved in the clinical trial. It is acceptable to use CRFs as source documents. If this is the case, it should be stated in this section what data will be collected on CRFs and what data will be collected from other sources.

The study case report form (CRF) is the primary data collection instrument for the study. All data requested on the CRF must be recorded. All missing data must be explained. If a space on the CRF is left blank because the procedure was not done or the question was not asked, write "N/D". If the item is not applicable to the individual case, write "N/A". All entries should be printed legibly in black ink. If any entry error has been made, to correct such an error, draw a single straight line through the incorrect entry and enter the correct data above it. All such changes must be initialed and dated. DO NOT ERASE OR WHITE OUT ERRORS. For clarification of illegible or uncertain entries, print the clarification above the item, then initial and date it.

12 Quality Assurance and Quality Control

QC procedures will be implemented beginning with the data entry system and data QC checks that will be run on the database will be generated. Any missing data or data anomalies will be communicated to the site(s) for clarification/resolution.

Following written SOPs, the monitors will verify that the clinical trial is conducted and data are generated, documented (recorded), and reported in compliance with the protocol, GCP, and the applicable regulatory requirements (e.g., Good Laboratory Practices (GLP), Good Manufacturing Practices (GMP)).

13 Ethics/Protection of Human Subjects

13.1 Ethical Standard

The investigator will ensure that this study is conducted in full conformity with Regulations for the Protection of Human Subjects of Research codified in 45 CFR Part 46, 21 CFR Part 50, 21 CFR Part 56, and/or the ICH E6.

13.2 Institutional Review Board

The protocol, informed consent form(s), recruitment materials, and all participant materials will be submitted to the IRB for review and approval. Approval of both the protocol and the consent form must be obtained before any participant is enrolled. Any amendment to the protocol will require review and approval by the IRB before the changes are implemented to the study. All changes to the consent form will be IRB approved; a determination will be made regarding whether previously consented participants need to be re-consented.

13.3 Informed Consent Process

13.3.1 Consent/Accent and Other Informational Documents Provided to Participants

Consent forms describing in detail the study agent, study procedures, and risks are given to the participant and written documentation of informed consent is required prior to starting intervention/administering study product. The following consent materials are submitted with this protocol:

13.3.2 Consent Procedures and Documentation

Informed consent is a process that is initiated prior to the individual's agreeing to participate in the study and continues throughout the individual's study participation. Extensive discussion of risks and possible benefits of participation will be provided to the participants and their families. Consent forms will be IRB-approved and the participant will be asked to read and review the document. The investigator will explain the research study to the participant and answer any questions that may arise. All participants will receive a verbal explanation in terms suited to their comprehension of the purposes, procedures, and potential risks of the study and of their rights as research

participants. Participants will have the opportunity to carefully review the written consent form and ask questions prior to signing. The participants should have the opportunity to discuss the study with their surrogates or think about it prior to agreeing to participate. The participant will sign the informed consent document prior to any procedures being done specifically for the study. The participants may withdraw consent at any time throughout the course of the trial. A copy of the signed informed consent document will be given to the participants for their records. The rights and welfare of the participants will be protected by emphasizing to them that the quality of their medical care will not be adversely affected if they decline to participate in this study.

A copy of the signed informed consent document will be stored in the subject's research record. The consent process, including the name of the individual obtaining consent, will be thoroughly documented in the subject's research record. Any alteration to the standard consent process (e.g. use of a translator, consent from a legally authorized representative, consent document presented orally, etc.) and the justification for such alteration will likewise be documented.

13.4 Participant and Data Confidentiality

Information about study subjects will be kept confidential and managed according to the requirements of the Health Insurance Portability and Accountability Act of 1996 (HIPAA). Those regulations require a signed subject authorization informing the subject of the following:

- What protected health information (PHI) will be collected from subjects in this study
- Who will have access to that information and why
- Who will use or disclose that information
- The rights of a research subject to revoke their authorization for use of their PHI.

In the event that a subject revokes authorization to collect or use PHI, the investigator, by regulation, retains the ability to use all information collected prior to the revocation of subject authorization. For subjects that have revoked authorization to collect or use PHI, attempts should be made to obtain permission to collect at least vital status (i.e. that the subject is alive) at the end of their scheduled study period.

Participant confidentiality is strictly held in trust by the participating investigators, their staff, and the sponsor(s) and their agents. This confidentiality is extended to cover testing of the clinical information relating to participants. Therefore, the study protocol, documentation, data, and all other information generated will be held in strict confidence. No information concerning the study or the data will be released to any unauthorized third party without prior written approval of the sponsor.

The study monitor, other authorized representatives of the sponsor, or representatives of the IRB may inspect all documents and records required to be maintained by the investigator, including but not limited to, medical records (office, clinic, or hospital) and pharmacy records for the participants in this study. The clinical study site will permit access to such records.

The study participant's contact information will be securely stored at each clinical site for internal use during the study. At the end of the study, all records will continue to be kept in a secure location for as long a period as dictated by local IRB and Institutional regulations.

Study participant research data, which is for purposes of statistical analysis and scientific reporting, will be stored on TrialMaster. This will not include the participant's contact or identifying information. Rather, individual participants and their research data will be identified by a unique study identification number. The study data entry and study management systems used by the clinical site and by research staff will be secured and password protected. At the end of the study, all study databases will be de-identified and archived with the Study Investigator and Principal Investigator.

Data will not be shared with additional investigators or third parties without prior approval from the participant. We will conform to any institutional, state, or federal auditors need to access data upon reasonable request.

13.5 Future Use of Data

Data collected for this study will be analyzed and stored at NYULMC. After the study is completed, the de-identified, archived data will be transmitted to and stored at NYIULMC controlled cloud services (e.g., Google Drive), under the supervision of [name], for use by other researchers including those outside of the study.

During the conduct of the study, an individual participant can choose to withdraw consent to have data stored for future research. When the study is completed, access to study data and/or samples will be provided through the NYIULMC controlled cloud services.

14 Data Handling and Record Keeping

14.1 Data Collection and Management Responsibilities

Data are collected from four sources:

- Six degree of freedom hand position. The 3-dimensional position and 3-dimensional rotation of both Oculus Rift touch controllers. Type: electronic
- 6-channel electromyography (EMG). EMG muscle activity of the biceps, triceps, and anterior deltoid (bilaterally). Type: electronic
- Demographic and characteristic data such as age, sex, height, weight, handedness, time since stroke, and arm length. Type: paper
- Medical records will be used to determine the type (ischemic vs. hemorrhagic) and location (cortical, subcortical, left vs. right) of stroke. Medical records will also be used to access the subject's acute DWI imaging. Type: electronic

Data collection is the responsibility of the clinical trial staff at the site under the supervision of the site PI. The investigator is responsible for ensuring the accuracy, completeness, legibility, and timeliness of the data reported.

All source documents should be completed in a neat, legible manner to ensure accurate interpretation of data. Black ink is required to ensure clarity of reproduced copies. When making changes or corrections, cross out the original entry with a single line, and initial and date the change. DO NOT ERASE, OVERWRITE, OR USE CORRECTION FLUID OR TAPE ON THE ORIGINAL.

Copies of the electronic CRF (eCRF) will be provided for use as source documents and maintained for recording data for each participant enrolled in the study. Data reported in the eCRF derived from source documents should be consistent with the source documents or the discrepancies should be explained and captured in a progress note and maintained in the participant's official electronic study record.

Clinical data (including AEs, concomitant medications, and expected adverse reactions data) and clinical laboratory data will be entered into TrialMaster, a 21 CFR Part 11-compliant data capture system. The data system includes password protection and internal quality checks, such as automatic range checks, to identify data that appear inconsistent, incomplete, or inaccurate. Clinical data will be entered directly from the source documents.

